The MITRAL Trial: Mitral
Implantation of TRAnscatheter
vaLves (Data Coordinating
Center)

NCT02370511

September 20, 2017

IRB Minimal Risk Protocol Template

Note: If this study establishes a human specimen repository (biobank) for research purposes, do not use this template. Use the Mayo Clinic Human Specimen Repository Protocol Template found on the IRB home page under Forms and Procedures at <http://intranet.mayo.edu/charlie/irb/>

First-time Use: Use this template to describe your study for a new IRB submission.

1. Complete the questions that apply to your study.
2. Save an electronic copy of this protocol for future revisions.
3. When completing your IRBe application, you will be asked to upload this document to the protocol section.

Modification: To modify this document after your study has been approved:

1. Open your study in IRBe. Click on the study 'Documents' tab and select the most recent version of the protocol. Save it to your files.
2. Open the saved document and activate "Track Changes".
3. Revise the protocol template to reflect the modification points, save the template to your files
4. Create an IRBe Modification for the study and upload the revised protocol template.

General Study Information

Principal Investigator: [name]

Study Title: The MITRAL Trial: Mitral Implantation of TRAnscatheter vaLves (Data Coordinating Center)

Protocol version number and date: Version 3, 12-19-218

Research Question and Aims

Purpose

The purpose of this trial is to establish the safety and feasibility of the Edwards SAPIEN XT TM and SAPIEN 3 devices and delivery systems in patients with severe symptomatic calcific mitral valve disease with severe mitral annular calcification and patients with failing mitral surgical rings of bioprostheses who are not candidates for mitral valve surgery.

Mayo Clinic as Data Coordinating Center for the MITRAL trial

This clinical trial was initiated at Northshore University by [name] before being recruited to Mayo Clinic in June 2018. When the trial was initiated, Mayo Clinic was a subsite and the study was approved under IRB 14-009069 with [name] as the principal investigator. The trial commenced enrollment on March 2015 and enrollment was completed December 2017. All enrolled patients have been treated and the trial is currently at the one-year follow up stage for all remaining patients. This clinical trial is being transferred to

the Mayo clinic and we will be the data coordinating center for this trial going forward. Please see coordinating center documents for sites list and data management plan.

Study Design and Methods

Design

As of [name] recruitment to Mayo on June 2018, all remaining patients in this trial are at the 1-year follow-up stage or beyond. These visits will be conducted at the respective sites in accordance to the procedural protocol and under approved IRBs at the different sites. The data gathered at the follow up visits will be entered into the existing electronic data capture database. Mayo Clinic staff will gather the data collected at all sites for analysis, and work with the sites to address any issues or protocol deviations.

Plan for collection and management of data from all centers:

The electronic case report forms (e-CRFs) are designed to accommodate the study design and requirements. Modification of e-CRFs will only be made if deemed necessary by the sponsor investigator. Primary data collection based on source documented hospital chart reviews will be performed by study coordinators at each clinical site. Electronic CRFs will be completed online. All applicable eCRFs will be automatically available to the study coordinator at the sites as new patients are enrolled in the study. All clinical sites will be monitored periodically by the Mayo Clinic staff for protocol adherence, accuracy of e-CRFs, and compliance to applicable regulations. Evident patterns of non-compliance with respect to these standards will be cause for the site to be put on probation. If corrective actions are not subsequently undertaken, the clinical site will be asked to withdraw from the trial.

The online database will reside on a central server accessible through the Internet by Mayo Clinic staff. Conventional data verification sub-routines will be extensively programmed to test entry and logical errors, while all individual (study patient based) case report forms will be linked for cross-reference. Periodic analysis of each data field (across cases) will be performed in order to examine the expected distributions of data, and to identify outliers for possible data errors. All e-CRFs will be subjected to initial inspection for omitted data, data inconsistencies, and deviations. The resolution of data inconsistencies will be done using electronic tracking and will be resolved by the clinical site.

Process for reporting and evaluating protocol events and deviations from all centers:

The patients will be followed closely by their cardiologist per standard of care in addition to scheduled visits per study protocol. All adverse events (AEs) will be reported by the Investigators and reviewed by the Sponsor in compliance with applicable regulations. For the purpose of this study, an adverse event is any undesirable medical occurrence in a patient. This definition does not depend on a causal relationship with the device or the protocol requirements. Expected clinical and non-significant clinical adverse events will not be reported. Adverse events may be volunteered by patients, elicited by the Investigator or designee, or collected via observation by the Investigator. All AEs will be assessed by the Investigator who will determine whether or not the event is related to the device and/or procedure, and whether or not the event meets serious criteria. If it is

determined that an AE has occurred, the investigator should obtain all the information required to complete the AE Form of the CRF. Source documents will be acquired by Mayo Clinic staff and provided to the Clinical Event Adjudication Committee (CEC) in a timely manner to ensure timely assessment and adjudication of the event as appropriate. In addition, patients will be instructed to contact the investigator, and/or study coordinator if any significant adverse events occur between study visits.

The investigators at each site will not deviate from the protocol without the prior written approval of the sponsor investigator except in medical emergencies or in unforeseen, isolated instances where minor changes are made that will not increase the patient's risk or affect the validity of the trial. In medical emergencies, prior approval for protocol deviations will not be required, but the sponsor investigator must be notified within 2 days of the incident. Periodic monitoring of protocol compliance will be performed for each site. The Sponsor has the right to suspend enrollment at sites deemed to have excessive protocol compliance issues.

Resources: *Describe the available resources to conduct the research (personnel, time, facilities, mentor commitment, etc.):*

(1a) This is a multisite study involving Mayo Clinic and non Mayo Clinic sites. *When checked, describe in detail the research procedures or activities that will be conducted by Mayo Clinic study staff.*

(1b) Mayo Clinic study staff will be engaged in research activity at a non Mayo Clinic site. *When checked, provide a detailed description of the activity that will be conducted by Mayo Clinic study staff.*

Subject Information

Target accrual is the proposed total number of subjects to be included in this study at Mayo Clinic. A "Subject" may include medical records, images, or specimens generated at Mayo Clinic and/or received from external sources.

Target accrual: 91 patients (31 patients per arm – Native Mitral Valve Arm, Valve-in-Ring arm, Valve-in-Valve arm)

Subject population:

Patients are 22 years of age or older with severe calcific native mitral valve stenosis, a failing surgical ring in the mitral position, or a failing surgical bioprosthesis in the mitral position who are not candidates for mitral valve surgery.

Inclusion Criteria

Patients that are currently enrolled in the MITRAL trial.

Exclusion Criteria

Patient not enrolled in the MITRAL trial.

Research Activity

Check all that apply and complete the appropriate sections as instructed.

1. **Drug & Device:** Drugs for which an investigational new drug application is not required. Device for which (i) an investigational device exemption application is not required; or the medical device is cleared/approved for marketing and being used in accordance with its cleared/approved labeling. (Specify in the Methods section)
2. **Blood:** Collection of blood samples by finger stick, heel stick, ear stick, or venipuncture.
3. **Biological specimens other than blood:** Prospective collection of human biological specimens by noninvasive means that may include: urine, sweat, saliva, buccal scraping, oral/anal/vaginal swab, sputum, hair and nail clippings, etc.
4. **Tests & Procedures:** Collection of data through noninvasive tests and procedures routinely employed in clinical practice that may include: MRI, surface EEG, echo, ultrasound, moderate exercise, muscular strength & flexibility testing, biometrics, cognition testing, eye exam, etc. (Specify in the Methods section)
5. **Data** (medical record, images, or specimens): Research involving use of existing and/or prospectively collected data.
6. **Digital Record:** Collection of electronic data from voice, video, digital, or image recording. (Specify in the Methods section)
7. **Survey, Interview, Focus Group:** Research on individual or group characteristics or behavior, survey, interview, oral history, focus group, program evaluation, etc. (Specify in the Methods section)

NIH has issued a *Certificate of Confidentiality* (COC). *When checked, provide the institution and investigator named on the COC and explain why one was requested.* _____

Biospecimens – Categories 2 and 3

(2) Collection of blood samples. When multiple groups are involved copy and paste the appropriate section below for example repeat section b when drawing blood from children and adults with cancer.

a. **From healthy, non-pregnant, adult subjects who weigh at least 110 pounds.** For a minimal risk application, the amount of blood drawn from these subjects may not exceed 550ml in an 8 week period and collection may not occur more frequently than 2 times per week.

Volume per blood draw: _____ ml

Frequency of blood draw (e.g. single draw, time(s) per week, per year, etc.) _____

b. **From other adults and children considering age, weight, and health of subject.** For a minimal risk application, the amount of blood drawn from these subjects may not exceed the lesser of 50 ml or 3 ml per kg in an 8 week period, and collection may not occur more frequently than 2 times per week.

Volume per blood draw: _____ ml

Frequency of blood draw (e.g. single draw, time(s) per week, per year, etc.) _____

(3) Prospective collection of biological specimens other than blood: _____

Review of medical records, images, specimens – Category 5

For review of existing data: provide a date range or an end date for when the data was generated. The end date can be the date this application was submitted to the IRB. Example: *01/01/1999 to 12/31/2015* or all records through *mm/dd/yyyy*.

Date Range:

Check all that apply (data includes medical records, images, specimens).

(5a) Only data that exists before the IRB submission date will be collected.

(5b) The study involves data that exist at the time of IRB submission **and** data that will be generated after IRB submission. Include this activity in the Methods section.

Examples

- The study plans to conduct a retrospective chart review and ask subjects to complete a questionnaire.
- The study plans to include subjects previously diagnosed with a specific disease and add newly diagnosed subjects in the future.

(5c) The study will use data that have been collected under another IRB protocol. Include in the Methods section and enter the IRB number from which the research material will be obtained. *When appropriate, note when subjects have provided consent for future use of their data and/or specimens as described in this protocol.*

Enter one IRB number per line, add more lines as needed

Data Specimens Data & Specimens _____

Data Specimens Data & Specimens _____

Data Specimens Data & Specimens _____

(5d) This study will obtain data generated from other sources. Examples may include receiving data from participating sites or an external collaborator, accessing an external database or registry, etc. Explain the source and how the data will be used in the Methods section.

(6) Video audio recording: *Describe the plan to maintain subject privacy and data confidentiality, transcription, store or destroy, etc.*

HIPAA Identifiers and Protected Health Information (PHI)

Protected health information is medical data that can be linked to the subject directly or through a combination of indirect identifiers.

Recording identifiers (including a code) during the conduct of the study allows you to return to the medical record or data source to delete duplicate subjects, check a missing or questionable entry, add new data points, etc. De-identified data is medical information that has been stripped of all HIPAA identifiers so that it cannot be linked back to the subject. De-identified data is **rarely** used in the conduct of a research study involving a chart review.

Review the list of subject identifiers below and, if applicable, check the box next to each HIPAA identifier being recorded at the time of data collection or abstraction. Identifiers apply to any subject enrolled in the study including Mayo Clinic staff, patients and their relatives and household members.

Internal refers to the subject's identifier that will be recorded at Mayo Clinic by the study staff.

External refers to the subject's identifier that will be shared outside of Mayo Clinic.

Check all that apply:	INTERNAL	EXTERNAL
Name		
Mayo Clinic medical record or patient registration number, lab accession, specimen or radiologic image number		
Subject ID, subject code or any other person-specific unique identifying number, characteristic or code that can link the subject to their medical data	Yes	
Dates: All elements of dates [month, day, and year] directly related to an individual, their birth date, date of death, date of diagnosis, etc.	Yes	
Note: Recording a year only is not a unique identifier.		
Social Security number		
Medical device identifiers and serial numbers	Yes	
Biometric identifiers, including finger and voice prints, full face photographic		

images and any comparable images		
Web Universal Resource Locators (URLs), Internet Protocol (IP) address numbers, email address		
Street address, city, county, precinct, zip code, and their equivalent geocodes		
Phone or fax numbers		
Account, member, certificate or professional license numbers, health beneficiary numbers		
Vehicle identifiers and serial numbers, including license plate numbers		
Check 'None' when none of the identifiers listed above will be recorded, maintained, or shared during the conduct of this study. (exempt category 4)	 None	 None

Data Analysis

The analysis of clinical outcomes will be based on the principle of intention to treat. There will be three intervention groups in the study: 1) Native Mitral Valve and 2) Valve-in-Ring and 3) Valve-in-Valve. The three groups will be evaluated separately for the primary and secondary outcomes.

Sample Size

Using a sample size of 30 total patients and a 2-sided alpha level of 0.05, the McNemar matched pairs test would have a power of 0.80 to detect an underlying pre to post change in proportions of 0.30 (i.e., proportions of 0.35 at pre versus 0.65 at post). Using the same sample size and alpha level, the paired t-test would have a power of 0.80 to detect an underlying effect size of 0.53 (i.e., a mean change which is 0.53 times the size of the corresponding standard deviation) for comparing pre and post change in continuous variables. A total of 30 patients in each group will be enrolled in this preliminary feasibility study.

Analysis and reporting of results:

The technical success, hemodynamics results and clinical outcomes will be analyzed and reported. The primary objective is to evaluate the short-term (<30 days) and mid term (12 months) safety and feasibility of transcatheter mitral valve implantation to treat severe calcific mitral valve disease or failing surgical mitral rings or bioprostheses in patients who are not candidates for standard surgical mitral valve replacement. The primary safety and effectiveness endpoints will be analyzed on an intention- to-treat basis. Therefore, all patients will be included in the analysis regardless of subsequent events.

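### The adverse-event section requires every event to be reported, then exempts expected and non-significant ones, without protecting serious, related or safety-endpoint events

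*Combined protocol and SAP*

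**What the plan says.** All the conflicting sentences stand in one section of the combined protocol and SAP, *Process for reporting and evaluating protocol events and deviations from all centers*:

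- General rule: "All adverse events (AEs) will be reported by the Investigators and reviewed by the Sponsor in compliance with applicable regulations".
- Definition: "For the purpose of this study, an adverse event is any undesirable medical occurrence in a patient". The next sentence adds that causality plays no part in it.
- Exemption: "Expected clinical and non-significant clinical adverse events will not be reported".
- Assessment: "All AEs will be assessed by the Investigator who will determine whether or not the event is related to the device and/or procedure". The same sentence requires a judgement of seriousness.
- Recording: if it is "determined that an AE has occurred, the investigator should obtain all the information required to complete the AE Form of the CRF".
- Adjudication: "Source documents will be acquired by Mayo Clinic staff and provided to the Clinical Event Adjudication Committee (CEC) in a timely manner".

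On timing, the coordinating-center section states: "The trial commenced enrollment on March 2015 and enrollment was completed December 2017". It continues: "All enrolled patients have been treated and the trial is currently at the one-year follow up stage for all remaining patients". The *Design* section adds that in June 2018 everyone still in follow-up had reached the one-year point or passed it, and that visits follow a separate procedural protocol. A data management plan is also referred to. Neither document was supplied. *Analysis and reporting of results* makes safety at <30 days and at 12 months part of the primary objective, but does not list the components of the safety endpoint.

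**The concern.** Under the section's own definition, an expected event is an AE, and so is a trivial one. A rule that all AEs are reported and a rule that these are not cannot both hold. The repetition of the word clinical suggests two separate exemptions, one for expected events and one for non-significant events. On that reading, expectedness alone is enough to leave out an event, however serious it is.

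The patients are not candidates for mitral valve surgery, so a site could readily regard some serious events as expected. With neither term defined, sites could also draw the line in different places. If an endpoint event went unreported and was caught nowhere else, the safety rate would fall. The intention-to-treat rule would not help: it keeps the patient in the denominator but does not restore the event to the numerator.

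**Working it through.** **Step 1. The text.** The plan gives no figure to reproduce here, so the first check is a comparison of sentences.

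| Sentence | Does an expected serious event get through? |
|---|---|
| All AEs reported | Yes |
| Exemption, read as two categories | No |
| Exemption, read as events both expected and non-significant | Yes, if a serious event counts as significant |
| All AEs assessed for relatedness and seriousness | Assessed; the text does not say what follows if it is also exempt |
| AE Form information obtained once an AE has occurred | Yes, read literally |
| Source documents to the CEC | Only if the event comes to the coordinating center's notice |

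Both readings of the exemption conflict with the general rule. Only the two-category reading reaches serious events. No sentence in the supplied text exempts serious, related or endpoint events from it.

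**Step 2. How much endpoint follow-up this version can govern.**

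Inputs from the documents: enrollment March 2015 to December 2017; transfer in June 2018; 30 patients in each of three groups (*Sample Size*), so 90; windows of <30 days and 12 months. Assumptions: treatment at enrollment, even accrual, no deaths or dropout, and text in force from June 2018.

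- *<30 days.* The latest possible treatment date is 31 December 2017. Adding 30 days gives 30 January 2018, before June 2018. Share governed: 0%.
- *12 months, Design section taken literally.* If everyone still in follow-up was at one year or beyond in June 2018, no 12-month time was open. Share: about 0%.
- *12 months, late-treated patients still short of one year.* Planned time is 90 × 12 = 1080 patient-months. Share = (fraction treated after June 2017) × (mean months still open ÷ 12).
  - Central case, mid-month dates: accrual lasts 33 months; 6/33 = 18.2%, or 16.4 of 90 patients; on average 3 months are open. 0.182 × 3/12 = 4.5%, or 49 of 1080 patient-months.
  - Low, from month boundaries: 5/32 × 2.5/12 = 3.3% (14.1 patients).
  - High, from month boundaries: 7/34 × 3.5/12 = 6.0% (18.5 patients).
  - Late accrual, assuming half of all patients treated in the last six months: 0.50 × 3/12 = 12.5%.
- *12 months, text in force only from its version date.* The date is misprinted; read as 19 December 2018 (assumption), a patient treated on 31 December 2017 has at most 12 days open. Share: about 0.02% of planned time.

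**Step 3. What one omitted patient would do.** If a patient's only qualifying event were missed, the group's rate would fall by 1/30 = 3.3 percentage points, or 1/31 = 3.2 points with the 31 per arm given under *Subject Information*. This is a unit of sensitivity, not an estimate: the documents give no event rates and no list of expected events.

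**The case against.** The best defence is that the section separates recording from reporting. The AE Form step is triggered when an AE has occurred, not when it is reportable, and all AEs are assessed for seriousness. Read literally, an expected serious event still has its form information collected, and the exemption may concern only onward reporting to the sponsor. The exemption can also be read as covering only events that are both expected and non-significant. That fits the instruction, in the same section, that patients call about significant events. Chart review by site coordinators is the main data collection route, and nothing says that endpoint events are found only through AE forms. Finally, this is a coordinating-center submission written after all patients had been treated.

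Most of this stands, and it limits the consequence. A reader might infer that the <30-day and 12-month safety rates are biased downward. The documents do not support that: they show neither that events were lost nor that endpoint capture depends on the exempted route.

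The defence does not remove the contradiction. No safeguard is worded as an exception, and the reference to regulations is attached to the general rule, not to the exemption. Monitoring for protocol adherence may not flag a site that applies the exemption as written, and inspecting forms for omitted data need not reveal a form that was never opened.

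**Conclusion.** The point holds as a contradiction in a stated safety-reporting rule, and it should be fixed. Confidence is high for the conflict in the text. The size of any bias cannot be determined and may be zero.

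Direct reach into the primary windows is 0% at <30 days and near zero at 12 months. The 4.5% figure (3.3–6.0%) needs even accrual and late-treated patients still short of one year in June 2018; 12.5% needs the late-accrual assumption as well. Both sit badly with the literal wording of the *Design* section, although enrollment running to December 2017 leaves room for such patients. The percentages measure follow-up time, not missed events.

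This version therefore acts mainly on events around and after one year. A reader might go further, because the text still speaks of newly enrolled patients and of suspending enrollment, which hints at wording carried over from an earlier document. That is a reason to check the procedural protocol, not evidence that it has the same sentence.

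**What to change.** Keep the exemption but limit it, for example: *Every event that is serious, device- or procedure-related, or that meets or could meet a safety endpoint is recorded on the AE Form and sent to the CEC regardless of expectedness. Only non-serious, unrelated, non-endpoint events judged clinically insignificant may be omitted.* Deleting the sentence outright would also remove the contradiction, but sites would then have to report every trivial occurrence.

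Check the procedural protocol and the data management plan for the same wording and reconcile the documents. Only if the sentence is there, use the monitoring already planned to look for omitted serious or endpoint events before analysis.

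The cost is a short protocol modification and a reading of two existing documents. If the wording is found, add some source checking, possibly some late AE entry, and perhaps slightly less favourable event rates. No new patients or procedures are needed.

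### Does the inclusion rule for currently enrolled patients remove earlier deaths and withdrawals from the intention-to-treat analysis?

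*Combined protocol and SAP*

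**What the plan says.** Two parts of the combined protocol and SAP bear on who is counted.

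- **Subject Information.** The sole inclusion criterion is "Patients that are currently enrolled in the MITRAL trial" and the sole exclusion criterion is "Patient not enrolled in the MITRAL trial". The accrual line reads "Target accrual: 91 patients (31 patients per arm", followed by the names of the three arms. The template text above it says that a subject may be a medical record, an image or a specimen.
- **Data Analysis, and Analysis and reporting of results.** "The analysis of clinical outcomes will be based on the principle of intention to treat". On the primary safety and effectiveness endpoints: "Therefore, all patients will be included in the analysis regardless of subsequent events". The primary objective covers outcomes before 30 days and at 12 months. Sample Size plans 30 patients in each group.

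The background on the data coordinating center gives the timing: "The trial commenced enrollment on March 2015 and enrollment was completed December 2017", and "All enrolled patients have been treated and the trial is currently at the one-year follow up stage for all remaining patients". The Design section adds that, as of June 2018, "all remaining patients in this trial are at the 1-year follow-up stage or beyond". June 2018 is when the investigator moved to the coordinating center. The trial is described as being transferred, without a date.

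**The concern.** The text mentions June 2018, so it was written at least five months after enrolment closed. A patient who died in 2016 was enrolled, but in ordinary speech is not *currently* enrolled. The intention-to-treat sentence may not rescue that patient, because it can be read as covering only what happens after someone has entered the set. If the inclusion criterion decides who enters, an earlier death is never a later event in an included patient.

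The stakes under that reading would be high. Being in the set would require having survived to the date of writing. Mortality at 30 days and at 12 months, both part of the primary objective, would be reported for survivors under an intention-to-treat label. Technical success would lose anyone who died at or soon after the procedure.

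A related gap is that the only tests named, McNemar and the paired t-test, need both a pre and a post value. The documents do not say how a patient without a post value enters such a comparison.

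**Working it through.** **1. The plan's own power figure.** Inputs from Sample Size: n = 30, two-sided alpha 0.05, effect size 0.53, proportions 0.35 and 0.65.

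- Paired t-test: noncentral t with 29 degrees of freedom and noncentrality 0.53 × √30 = 2.90. Power is 0.801, against 0.80 stated.
- McNemar (asymptotic): Φ[(√n × 0.30 − 1.96√ψ) / √(ψ − 0.09)], where ψ is the discordant proportion. The plan does not state ψ. Power is 0.80 at ψ = 0.372: (1.643 − 1.196) / 0.531 = 0.84, and Φ(0.84) = 0.80.

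Both figures rest on 30 per group, the planned full cohort.

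**2. What the literal reading would do.**

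- 30 days: the latest possible enrolment is 31 December 2017, and 30 days later is 30 January 2018. From there to 1 June 2018, the earliest date *currently* can mean, is 122 days. Nobody who died within 30 days could be in the set.
- 12 months: assume even accrual from 1 March 2015 to 31 December 2017 (1,037 days). By 1 June 2018, 79% of patients would have passed 365 days, and 94% of the 12-month at-risk time would have elapsed.
- Illustration for an arm of 31. The deaths are assumed, since the documents give none. The upper limit for zero events in n is 1 − 0.025^(1/n).

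| Assumed earlier deaths | All-patient mortality | Literal reading | Exact 95% upper limit |
|---|---|---|---|
| 3 | 3/31 = 9.7% | 0/28 | 12.3% |
| 6 | 6/31 = 19.4% | 0/25 | 13.7% |
| 9 | 9/31 = 29.0% | 0/22 | 15.4% |

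The arithmetic is right, but it shows only what would follow if the literal reading were used.

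**3. Which reading the documents support.**

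- *Where the rule sits.* The criterion describes the subjects of an IRB filing. No sentence defines the analysis set by it. The sections that do say who is analysed include all patients.
- *Usage of enrolled.* The background uses *enrolled* for everyone who entered and *remaining* for those still in follow-up. The criterion uses *enrolled*.
- *The pair of criteria.* Inclusion says currently enrolled and exclusion says not enrolled. The two cover every patient only if they mean the same thing by enrolled. Otherwise a patient who entered and died falls under neither.
- *Accrual.* Planned: 3 × 30 = 90. Per-arm figure in the accrual line: 3 × 31 = 93. Stated total: 91. If as many as 93 had entered, a survivors-only set of 91 would leave room for 93 − 91 = 2 losses across all arms since March 2015. If 90 had entered, it would leave none. The target is a whole-cohort number.
- *Definition of subject.* A record qualifies, so a subject need not be alive or in follow-up.
- *Objective.* Every 30-day window had closed before the text was written. The literal reading would empty half of the primary objective.
- *Data flow.* The coordinating center takes over the existing database and gathers what all sites collected. Nothing calls for removing records.

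**The case for a change.** The best case for a change is that intention to treat does not by itself say who enters the set. No sentence defines the cohort as everyone enrolled from March 2015 to December 2017, and no count actually enrolled is given. The subject section is the only place with formal entry criteria. A single clause would settle the matter at almost no cost.

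Part of this stands. *Currently* is a loose word, and a sentence naming the cohort would read better. The 90, 91 and 93 figures do not agree, so the denominator cannot be confirmed from the text.

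The step from there to excluded deaths does not stand. It needs an analyst to import an IRB-form criterion into the analysis, over an explicit statement that all patients are included, and to produce a 30-day safety result that could not contain a death. In a study without randomised comparison, events subsequent to enrolment is the natural meaning of the intention-to-treat sentence. The case also leans on a June 2018 transfer date that the documents do not give.

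The missing rule for absent post values is a gap in detail. The tests appear only in the sample-size statement, and the procedural protocol that the Design section refers to is not available here and may hold the rule. An analyst would report the number of pairs beside each paired result and count deaths in the safety outcomes.

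**Conclusion.** No change follows. The plan's operative rule is that all patients are analysed, and the accrual target, the exclusion line, the definition of a subject and the 30-day objective all fit the full enrolled cohort. On that reading the wording has no effect on any result: planned n stays at 30 per group and the stated power of 0.80 stands (for McNemar, given a discordant proportion near 0.37). The zero-mortality figures hold only under a reading that the documents disfavour, and the table also needs deaths that the documents do not report.

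The accrual mismatch is a clerical slip in a target figure, recorded after enrolment had closed, that the power statement does not use.

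This conclusion assumes that records of patients who died or left remain in the database being taken over. Nothing in the documents suggests otherwise.
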